8.1.3 DEFINITION OF UNANTICIPATED PROBLEMS (UP)

This definition could include an unanticipated adverse device effect, any serious adverse effect on health or safety or any life-threatening problem or death caused by, or associated with, a device, if that effect, problem, or death was not previously identified in nature, severity, or degree of incidence in the investigational plan or application (including a supplementary plan or application), or any other unanticipated serious problem associated with a device that relates to the rights, safety, or welfare of subjects (21 CFR 812.3(s)).

8.2 CLASSIFICATION OF AN ADVERSE EVENT

8.2.1 SEVERITY OF EVENT

Mild – Events require minimal or no treatment and do not interfere with the participant's daily activities.

Moderate – Events result in a low level of inconvenience or concern with the therapeutic measures. Moderate events may cause some interference with functioning.

Severe – Events interrupt a participant's usual daily activity and may require systemic drug therapy or other treatment. Severe events are usually potentially life-threatening or incapacitating.

8.2.2 RELATIONSHIP TO STUDY AGENT

The clinician's assessment of an AE's relationship to study agent (drug, biologic, device) is part of the documentation process, but it is not a factor in determining what is or is not reported in the study. If there is any doubt as to whether a clinical observation is an AE, the event should be reported. All AEs must have their relationship to study agent assessed. In a clinical trial, the study product must always be suspect. To help assess, the following guidelines are used.

Related – The AE is known to occur with the study agent, there is a reasonable possibility that the study agent caused the AE, or there is a temporal relationship between the study agent and event. Reasonable possibility means that there is evidence to suggest a causal relationship between the study agent and the AE.

Not Related – There is not a reasonable possibility that the administration of the study agent caused the event, there is no temporal relationship between the study agent and event onset, or an alternate etiology has been established.

8.2.3 EXPECTEDNESS

Expected adverse reactions are AEs that are common and known to occur for the study agent being studied. Expected adverse events in this study include pain, tenderness, purpura, persistent erythema, edema, burn, blistering, crusting, hyperpigmentation, hypopigmentation, scarring and potential for damage to hair follicles within the treatment area and subsequent loss of hair within the treatment area.

An AE or suspected adverse reaction is considered "unexpected" if it is not known to occur for the study agent being studied and at the specificity or severity that has been observed.

The sub-investigator (SI) will be responsible for determining whether an AE is expected or unexpected. An AE will be considered unexpected if the nature, severity, or frequency of the event is not consistent with the risk information previously described for the study agent.

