2.3 POTENTIAL RISKS AND BENEFITS

2.3.1 KNOWN POTENTIAL RISKS

The potential risks for adverse effects of the treatment procedure include but are not limited to temporary swelling, redness, pain and burns at treatment site. The following long range risks were also identified as low probability adverse events: scarring, skin breakdown and hyper or hypopigmentation.

Previous studies have shown the immediate risks outlined above are transient and generally well-tolerated by patients. The long-range risks outlined above are theoretical, as there have been no reports of these incidences.

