8.1.2 DEFINITION OF SERIOUS ADVERSE EVENTS (SAE)

An AE or suspected adverse reaction is considered "serious" if, in the view of either the investigator or sponsor, it results in any of the following outcomes: death, a life-threatening adverse event, inpatient hospitalization or prolongation of existing hospitalization, a persistent or significant incapacity or substantial disruption of the ability to conduct normal life functions, or a congenital anomaly/birth defect. Important medical events that may not result in death, be life-threatening, or require hospitalization may be considered serious when, based upon appropriate medical judgment, they may jeopardize the patient or subject and may require medical or surgical intervention to prevent one of the outcomes listed in this definition. Examples of such medical events include allergic bronchospasm requiring intensive treatment in an emergency room or at home, blood dyscrasias or convulsions that do not result in inpatient hospitalization, or the development of drug dependency or drug abuse.

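### Scarring and pigment change are listed as expected reactions in 8.2.3 but called theoretical and unreported in 2.3.1, leaving the incidence test for unanticipated effects without a settled reference

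*Combined protocol and SAP*

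**What the plan says.** Section 2.3.1 sets out the device's long-range risks: "The following long range risks were also identified as low probability adverse events: scarring, skin breakdown and hyper or hypopigmentation". It adds: "The long-range risks outlined above are theoretical, as there have been no reports of these incidences".

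Section 8.2.3 defines expectedness differently: "Expected adverse reactions are AEs that are common and known to occur for the study agent being studied". Its list of expected events includes "hyperpigmentation, hypopigmentation, scarring and potential for damage to hair follicles within the treatment area". The sub-investigator decides whether an event is expected. The section closes with a test: "An AE will be considered unexpected if the nature, severity, or frequency of the event is not consistent with the risk information previously described". A separate sentence in 8.2.3 also brings in the specificity or severity observed.

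Section 8.1.3 counts a serious device effect as unanticipated if it "was not previously identified in nature, severity, or degree of incidence in the investigational plan or application". It adds a residual category: "any other unanticipated serious problem associated with a device that relates to the rights, safety, or welfare of subjects".

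Under 8.4.2 every serious adverse event goes to the sponsor within 24 hours, whatever its expectedness, and a written report goes to the clinical monitor within seven working days. Those steps do not name the IRB. The IRB and the regulator come in through the provisions for unanticipated effects and problems in 8.4.2 and 8.4.3, with a limit of 10 working days.

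**The concern.** An event that has never been reported cannot also be common and known, so one of the two sections is wrong. The question is whether this is only untidy or whether it affects what gets reported.

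It can affect reporting at one point. Whether a serious device effect is unanticipated depends partly on whether its incidence was already identified in the plan, and here the plan gives two incompatible answers. If a sub-investigator relies on the list in 8.2.3, the first serious scar or pigment injury could be treated as anticipated. The IRB report and the sponsor's evaluation to the regulator could then be left out. The schedule makes a late finding conceivable: treatment ends at week 7 and the next planned visit is week 20 (7.3.7), so a scar might first be examined with no burn on record.

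**Working it through.** The plan states no figure on this point, so the check is a comparison of sections and a trace of the reporting routes.

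**Overlap of the two lists**
- Long-range risks in 2.3.1: scarring, skin breakdown, hyperpigmentation, hypopigmentation. Total 4.
- Expected events in 8.2.3: pain, tenderness, purpura, persistent erythema, edema, burn, blistering, crusting, hyperpigmentation, hypopigmentation, scarring, and hair-follicle damage with hair loss (counted as one). Total 12.
- In both lists: scarring, hyperpigmentation, hypopigmentation. Total 3. Only in 2.3.1: 4 − 3 = 1, skin breakdown.

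**What each test gives for a serious scar or pigment change**
- Nature: both sections name these events, so their nature is identified either way.
- Severity: neither section describes scarring or pigment change of a serious grade, for instance one causing "a persistent or significant incapacity or substantial disruption of the ability to conduct normal life functions" (8.1.2). 8.2.3 gives names without grades. This limb points to unanticipated under both sections.
- Frequency or incidence: the 8.2.3 list points to anticipated and 2.3.1 points to unanticipated. This is the unsettled limb.

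The limbs in 8.1.3 are joined by *or*, so failing one is enough. Read carefully, the severity limb should usually decide the matter.

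**Routes that name the IRB for an individual event**
1. Burn of any degree, or pain beyond narcotics (7.8): written report to the IRB chairman within 7 days. Not triggered if the event is not handled as a burn.
2. Minor complications such as appearance (7.8): reportable within 30 days and shared with the IRB chairman. Not triggered on its wording, because the event is serious.
3. Unanticipated effect or problem (8.4.2, 8.4.3): within 10 working days. Depends on the classification above.

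Of these 3 routes, only the third can carry a serious non-burn case, and one limb of its trigger rests on the contradictory text. Non-serious cases are outside the issue, because each limb stated in 8.1.3 requires seriousness.

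**The case against.** The strongest reply is that the 8.2.3 label does not control the IRB report. Section 8.1.3 does not use the word expected. It sets its own test, with severity as a sufficient ground, and 8.2.3 itself considers severity in two places. A reader might infer that listing scarring as expected stops the IRB report, or leaves a serious case open to either classification. The documents do not support that: nothing in them makes the label decisive, and the severity wording favours reporting under either section.

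There are also backstops. The sponsor learns of every serious event within 24 hours, 8.6 provides a medical monitor, and 8.5 gives serious events and severe reactions as examples that might prompt a safety review, with notice to the IRB if the study is halted. The device works by heating skin, so many device-caused scars would plausibly enter through the burn route; that is an inference, not a statement in the plan. The prior risk information meant in 8.2.3 is not tied to a named section, and the user manual and consent text, which are not available here, may bear on it.

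A reader might also see a gap in the absence of skin breakdown from the 8.2.3 list. It does no harm: the list is introduced as inclusive, and being off it favours an unexpected classification.

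Most of this stands, and it makes the consequence small. It does not remove the contradiction or settle the incidence limb, and the listed backstops do not themselves require an IRB report of an individual case.

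**Conclusion.** The contradiction is exact and in current text: 3 of the 4 long-range risks in 2.3.1 are also among the 12 expected events in 8.2.3, with incompatible statements of how often they occur. The consequence is a narrow residual risk. A serious, non-burn scar or pigment injury might be judged anticipated and so miss the 10-working-day route to the IRB and regulator. That requires the person classifying the event to rely on the list and to overlook the severity wording.

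The documents give no rate for such events and none is assumed here; they would probably be rare. The 24-hour report to the sponsor, burn reporting, ordinary adverse event recording and the handling of non-serious events are unaffected. This is a minor safety-reporting correction with no bearing on endpoints, sample size or analysis.

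**What to change.** In 8.2.3, take scarring, hyperpigmentation and hypopigmentation out of the main list and put them on a separate line, for example: *identified as possible, low probability, no prior reports; any serious occurrence is treated as unanticipated in severity and degree of incidence and is reported under 8.4.2–8.4.3*. Leave non-serious cases to ordinary adverse event recording; there is no need to class every first occurrence as unexpected.

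If the sponsor does hold reports of these events, correct 2.3.1 and check the consent risk text instead.

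The cost is a few sentences and possibly an occasional extra IRB report.

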8.3 TIME PERIOD AND FREQUENCY FOR EVENT ASSESSMENT AND FOLLOW-UP

The occurrence of an AE or SAE may come to the attention of study personnel during study visits and interviews of a study participant presenting for medical care, or upon review by a study monitor.

All AEs including local and systemic reactions not meeting the criteria for SAEs will be captured on the appropriate CRF. Information to be collected includes event description, time of onset, clinician's assessment of severity, relationship to study product (assessed only by those with the training and authority to make a diagnosis), and time of resolution/stabilization of the event. All AEs occurring while on study must be documented appropriately regardless of relationship. All AEs will be followed to adequate resolution.

Any medical condition that is present at the time that the participant is screened will be considered as baseline and not reported as an AE. However, if the study participant's condition deteriorates at any time during the study, it will be recorded as an AE. UPs will be recorded in the data collection system throughout the study.

Changes in the severity of an AE will be documented to allow an assessment of the duration of the event at each level of severity to be performed. AEs characterized as intermittent require documentation of onset and duration of each episode.

The PI will record all reportable events with start dates occurring any time after informed consent is obtained until 7 (for non-serious AEs) or 30 days (for SAEs) after the last day of study participation. At each study visit, the investigator will inquire about the occurrence of AE/SAEs since the last visit. Events will be followed for outcome information until resolution or stabilization.

8.4 REPORTING PROCEDURES

8.4.1 ADVERSE EVENT REPORTING

All AEs will be recorded on the appropriate CRF and will include information about the start and stop dates, severity and relatedness. There should be an attempt to report a “diagnosis” rather than the individual signs, symptoms and abnormal laboratory values associated with the diagnosis. However, a diagnosis should be reported only if, in the Investigator’s judgment, it is relatively certain (i.e., definite or possible). Otherwise individual signs, symptoms and abnormal laboratory values should be reported as distinct adverse events.

8.4.2 SERIOUS ADVERSE EVENT REPORTING

All serious AE, whether or not deemed expected or device related, must be reported to the sponsor’s clinical research department immediately or within 24 hours by telephone (see contact details below).

Name: [name], Director of Clinical Research

[contact] [name]

Email: [contact]

Address: [name]

A written report prepared by the Principal Investigator using the Serious Adverse Event or Serious Adverse Device Effect Report must follow within seven working days to the clinical monitor and should include a full description of the event and sequence.

The study investigator shall complete an Unanticipated Adverse Device Effect Form and submit to the study sponsor and to the reviewing IRB as soon as possible, but in no event later than 10 working days after the investigator first learns of the effect. The study sponsor contact information is provided in Section 1, Key Roles. The study sponsor is responsible for conducting an evaluation of an unanticipated adverse device effect and shall report the results of such evaluation to FDA, any other country regulatory authority and to all reviewing IRBs and participating investigators within 10 working days after the sponsor first receives notice of the effect. Thereafter the sponsor shall submit such additional reports concerning the effect as the applicable regulatory authority requests.

8.4.3 UNANTICIPATED PROBLEM REPORTING

Incidents or events that meet the criteria for UPs require the creation and completion of an UP report form. It is the site investigator's responsibility to report UPs to their IRB and to the study sponsor. The UP report will include the following information:

Protocol identifying information: protocol title and number, PI's name, and the IRB project number;

- A detailed description of the event, incident, experience, or outcome;
- An explanation of the basis for determining that the event, incident, experience, or outcome represents an UP;
- A description of any changes to the protocol or other corrective actions that have been taken or are proposed in response to the UP.

An investigator shall submit to the sponsor and to the reviewing IRB a report of any unanticipated adverse device effect occurring during an investigation as soon as possible, but in no event later than 10 working days after the investigator first learns of the effect (21 CFR 812.150(a)(1)). A sponsor who conducts an evaluation of an unanticipated adverse device effect under 812.46(b) shall report the results of such evaluation to the applicable regulatory authority and to all reviewing IRB's and participating investigators within 10 working days after the sponsor first receives notice of the effect. Thereafter the sponsor shall submit such additional reports concerning the effect as the applicable regulatory authority requests.

8.4.4 REPORTING OF PREGNANCY

Not applicable

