5 STUDY ENROLLMENT AND WITHDRAWAL

5.1 PARTICIPANT INCLUSION CRITERIA

In order to be eligible to participate in this study, an individual must meet all of the following criteria:

1. Healthy adult female subject at least 18 years of age and older with Fitzpatrick skin types I-IV who are willing to participate.
2. Women requesting treatment for skin laxity of the face.
3. Able to read, understand and voluntarily provide written Informed Consent.
4. Able and willing to comply with the treatment/follow-up schedule and requirements.
5. Ability to tolerate the RF/PEMF procedure, and willing to adhere to the treatment regimen.

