5.2 PARTICIPANT EXCLUSION CRITERIA

An individual who meets any of the following criteria will be excluded from participation in this study:

1. Having any active electrical implant anywhere in the body, such as a pacemaker or an internal defibrillator.
2. Having a permanent implant in the treated area.
3. Prior use of retinoids in treated area within 2 weeks of initial treatment or during the course of the study.
4. Use of oral Isotretinoin (Accutane®) within 6 months of initial treatment or during the course of the study.
5. Patient on systemic corticosteroid therapy 6 months prior to and during the course of the study.
6. Prior use of collagen, fat injections and /or other methods of skin augmentation (enhancement with injected or implanted material) in treated area within 4-6 weeks of initial treatment or during the course of the study. Treatment may not be performed at all over permanent dermal implants.
7. Prior ablative resurfacing procedure in treated area with laser or other devices within 12 months of initial treatment or during the course of the study.
8. Any other surgery in treated area within 12 months of initial treatment or during the course of the study.
9. History of keloid formation or poor wound healing in a previously injured skin area.
10. History of epidermal or dermal disorders (particularly if involving collagen or micro vascularity).
11. Open laceration or abrasion of any sort on the area to be treated.
12. History of immunosuppression/immune deficiency disorders (including HIV infection or AIDS) or use of immunosuppressive medications.

13. Having any form of active cancer at the time of enrollment and during the course of the study.
14. Significant concurrent illness, such as uncontrolled diabetes i.e. any disease state that in the opinion of the Investigator would interfere with the treatment, or healing process.
15. Participation in a study of another device or drug within 1 month prior to study enrollment or during this study, and as per the Investigator's careful discretion, as long as not contradictory to any of the above criteria.
16. Tattoos in the treatment area.
17. Mentally incompetent, prisoner or evidence of active substance or alcohol abuse.

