7 STUDY PROCEDURES AND SCHEDULE

7.1 STUDY PROCEDURES/EVALUATIONS

7.1.1 STUDY SPECIFIC PROCEDURES

- Medical history: obtained through interview. History will include age, other medical conditions, and previous invasive or non-invasive cosmetic procedure to the face or neck in the last 6 months.
- Medication history: current medications will be obtained through interview and will include prescription, over the counter, and herbal medications taken 4 weeks prior to study enrollment.
- Physical examination: completed by PI. Focused head and neck skin assessment that will include Fitzpatrick skin type and evidence of scars, infection, or inflammation of the face or neck.
- Imaging assessment: standard photos of the treated area will be taken by the PI using a Nikon D3100 using a 105 mm lens with fixed 2 Nikon flashes using diffuse bounce flash technique that reduces shadows and accentuates the subject's contours.
- Cutometer assessment at baseline, week 7 and at week 20.
- Rater assessment: The FWES will be used to rate the level of skin aging.
- Patient-reported outcomes: subjects will be asked to complete the GAIS questionnaire at weeks 7 and 20, and a 5-point Likert subject satisfaction scale at weeks 4, 7 and 20.

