7.3.7 SCHEDULE OF EVENTS TABLE

Procedures	Screening (Visit 1, Week 0)	Baseline (Visit 1, Week 0)	Follow-up (Visit 2, Week 1)	Follow-up (Visit 3, Week 2)	Follow-up (Visit 4, Week 3)	Follow-up (Visit 5, Week 4)	Follow-up (Visit 6, Week 5)	Follow-up (Visit 7, Week 6)	Follow-up (Visit 8, Week 7)	Final Study Visit (Visit 9, Week 20)
Informed Consent	X									
Eligibility assessment	X	X								
Demographics	X									
Medical History	X									
Physical exam	X									
Photographic imaging		X				X			X	X
Cutometer® readings		X							X	X
Administer treatment		X	X	X	X	X	X	X	X	
Immediate response		X	X	X	X	X	X	X	X	
Subject pain VAS		X	X	X	X	X	X	X	X	
Subject GAIS									X	X
Subject satisfaction						X			X	X
Adverse events		X	X	X	X	X	X	X	X	X
Concomitant medications		X	X	X	X	X	X	X	X	X

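### The trial enrols only women from age 18, yet no provision specifically asks about, records or follows a pregnancy, and section 8.4.4 sets pregnancy reporting aside without a reason

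*Combined protocol and SAP*

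**What the plan says.** The first inclusion criterion in protocol section 5.1 reads "Healthy adult female subject at least 18 years of age and older with Fitzpatrick skin types I-IV who are willing to participate". No criterion refers to menopausal status or contraception. Section 5.2 lists 17 exclusions, and none mentions pregnancy or nursing.

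Section 7.1.1 defines the medical history: "History will include age, other medical conditions, and previous invasive or non-invasive cosmetic procedure to the face or neck" (the procedures being those of the last 6 months). A medication history covering the 4 weeks before enrolment is taken as well. Laboratory evaluations do not apply (7.2.1), so no pregnancy test is done. The schedule of events (7.3.7) has no pregnancy row.

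Section 8.4.4, headed for pregnancy reporting, contains only "Not applicable". Section 8.1.2 includes among the outcomes that make an event serious "a persistent or significant incapacity or substantial disruption of the ability to conduct normal life functions, or a congenital anomaly/birth defect". Section 8.3 limits recording by the start date of the event: up to 7 days after the last day of participation for non-serious events, and up to 30 days for serious ones.

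**The concern.** An entry in 8.4.4 that pregnancy reporting does not apply would suit a trial in men or in post-menopausal women. Here every participant is a woman and the age range includes the child-bearing years, so the entry does not fit the population and no reason is given for it. It also sits badly with 8.1.2, which recognises a pregnancy outcome as a serious event but leaves the site no instruction that would lead it to one.

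What is at stake is participant protection and completeness of safety reporting. A woman who is pregnant at entry, or becomes so, could receive some or all of the eight treatments without anyone having asked. Her pregnancy could go unrecorded, and if uncomplicated it would not be followed to outcome.

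**Working it through.** This is mainly a reading check, following a pregnancy through the protocol.

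1. **At entry.** Pregnancy is named in 0 of 17 exclusions (5.2). The nearest is item 14, on significant concurrent illness, but that concerns disease states that would interfere with treatment or healing, and pregnancy is not a disease. Pregnancy is also absent from the listed history items (7.1.1). The question on other medical conditions and the medication history could reveal it, but neither asks about it.

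2. **During treatment.** Pregnancy is named in 0 of 14 schedule rows (7.3.7). Adverse events and medication changes are reviewed at every visit (7.3.3, 7.3.4, 8.3). Section 8.1.1 defines an adverse event as an untoward occurrence. An uncomplicated pregnancy does not clearly meet that definition, and no other section makes it recordable.

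3. **Once known.** Section 5.4.1 says the investigator may end participation when a medical condition or situation makes continuing contrary to the participant's interest. This is a permission. No section tells the site to stop treatment.

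4. **Outcome.** A complication recorded as an adverse event is followed to resolution or stabilization (8.3). An anomaly that the site hears of can be reported as a serious event (8.4.2). If judged an unanticipated device effect, it is reported within 10 working days of the investigator learning of it (8.4.2, 8.4.3). All these routes depend on the site hearing of the event, and none covers an uncomplicated pregnancy.

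5. **Does the 30-day window reach delivery?** Section 8.3 does not say how an anomaly is dated. Suppose it is dated at birth, and take the last day of participation as Visit 9. The longest time from consent to the close of serious-event recording uses:
   - up to 30 days from screening to baseline (7.3.1);
   - seven treatment intervals of at most 7 + 3 = 10 days (7.3.3);
   - 12 + 2 = 14 weeks, or 98 days, to Visit 9 (7.3.4);
   - 30 days of recording after that (8.3).

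   Sum: 30 + 7 × 10 + 98 + 30 = 228 days; 228 / 7 = 32.6 weeks.

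   Assumption, not in the documents: term birth is at 37 weeks' gestation or later, which is 37 − 2 = 35 weeks or more after conception. Then 35 − 32.6 = 2.4 weeks. A term delivery of any pregnancy conceived after consent therefore falls at least 2.4 weeks after recording closes. On the nominal schedule, recording closes 7 × 7 + 84 + 30 = 163 days, or 23.3 weeks, after first treatment.

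This result is narrow. It does not apply to an anomaly dated during gestation, to a preterm birth, to a woman already pregnant at consent (whose delivery may fall inside the window), or to the device-effect route, which runs from when the investigator learns of the effect.

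**The case against.** The strongest reply is that the protocol is less silent than it looks. The screening interview, the medication review at every visit (over-the-counter products included, 7.5), the adverse-event enquiry, and the invitation in 7.3.6 to contact the investigator could each bring a pregnancy to light. Section 5.4.1 already gives power to stop. Section 7.8 requires at least 2 years of follow-up for a device complication, which would outlast a delivery. The device is non-invasive, applied to the face and used within its approved indication, and the documents show no fetal hazard. The user manual cited in 7.3.2 and the consent forms listed in 13.3.1 are not visible here and may deal with pregnancy.

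Much of this stands, and it rules out stronger readings. A reader might infer that a pregnancy could surface only if the woman volunteered it, or that the investigator would be powerless to stop. The provisions above do not support either. A reader might also infer that the device endangers a fetus, or that no anomaly could ever be reported. The documents support neither: they contain no evidence on the first, and the routes in step 4 contradict the second.

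The core remains. The existing prompts work by chance, the power to stop is discretionary, and the 2-year rule begins with a device complication. None of them makes an uncomplicated pregnancy recordable or followed. If the manual or consent forms do mention pregnancy, 5.2 and 8.4.4 would need to agree with them.

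**Conclusion.** The point holds as a gap in participant selection and safety reporting: no provision specifically prompts the site to ask about, record or follow a pregnancy, and 8.4.4 gives no reason for setting the matter aside. It should be corrected because the correction is cheap and the present entry does not fit the population.

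Its reach is up to eight treatments per woman, in about 45 women and at most 60 (5.4.2). No probability is attached, because the documents give no pregnancy frequency or age distribution beyond the lower limit. A reader might take this as a threat to the trial's conclusions. It is not: the elasticity endpoint and its analysis do not depend on it, and 10.4.4 states that there are no formal safety endpoints. The timing result in step 5 is secondary, and the verdict would stand without it.

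**What to change.** 1. Add pregnancy to the exclusions in 5.2, and nursing only if the device labelling calls for it. Ask about pregnancy in the existing screening interview (7.1.1). With no hazard shown, the exclusion is precautionary, for an elective cosmetic treatment. It also brings a pregnancy found on study under the second ground in 5.4.1, a newly developed exclusion criterion.

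2. Replace the entry in 8.4.4 with a working rule: ask at the visits where adverse events are already asked about, record any pregnancy, stop treatment, and follow to outcome with the participant's consent. Section 5.4.2 already asks withdrawn subjects to complete the week 20 visit, so the first follow-up contact exists.

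3. Check the user manual and consent forms, and make them and the protocol agree.

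The cost is wording in three sections, one interview question, one CRF line, matching consent text and IRB approval (13.2), with possible re-consent if enrolment has begun. The downside is a few exclusions and occasional contact after study end. No test or extra visit is proposed. A spoken question will miss a pregnancy the woman does not yet know of, which is why it is repeated at each visit.
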